11.4.2 Statistical Methods

Treatment emergent lab abnormalities will be summarized in chemo-radiation phase and adjuvant phase separately and also in the overall study. For each of the continuous laboratory parameters, the following outputs will be produced for each treatment group:

- Summary of lab measurements at each scheduled visits
- Summary of changes from baseline at each post-baseline visits along with treatment group difference
- Shifts from baseline grades to worst post-baseline grades (only for the parameters where CTCAE grading is possible)
- The number and percentage of subjects with maximum treatment-emergent laboratory values meeting the potentially clinically significant criteria (excluding hepatic tests)
- For hepatic tests, the number and percentage of subjects with hepatic laboratory values meeting several cut-off values (e.g., $> 3 \times \text{ULN}$, $> 5 \times \text{ULN}$, $> 10 \times \text{ULN}$, etc.) specified for each test
- Listing of laboratory values for subjects with potentially clinically significant values

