14.4 Study Monitoring of Primary Objectives

Interim Reporting for the DMC

The Independent Data Monitoring Committee (IDMC), as coordinated by RTOG Foundation, will review the study at least twice a year with respect to subject accrual, pretreatment characteristics of accrued subjects, the frequency and severity of toxicities and morbidity. The IDMC is also available to review the study on an "as needed" basis.

Safety

AbbVie will assess adverse events, laboratory data and vital signs throughout the study. Analyses of adverse events will include only "treatment-emergent" events, i.e., those that start or worsen on or after the day of the first dose of study drug. Adverse event severity and laboratory evaluation changes will be assessed by utilizing National Cancer Institute (NCI) Common Terminology Criteria for Adverse Events (CTCAE) Version 4.0. Adverse events will be summarized by preferred terms within a System and Organ Class according to the most current Medical Dictionary for Regulatory Activities (MedDRA) dictionary. Changes from baseline will be analyzed for each scheduled post-baseline visit and for the final visit for blood chemistry and hematology parameters, as well as urinalysis and vital sign parameters. Shifts in laboratory values from baseline NCI CTCAE grades to maximum and final post-baseline grades will be assessed.

Interim Superiority and Futility Analysis of Efficacy Data

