7.3 Definition of Treatment Emergent Observation for Safety Analysis

For safety assessments, Treatment Emergent (TE) observations are defined as all newly occurring or worsening safety observation with onset at or following the initiation (date and time) of any study drug and no later than 49 days after the last dose of Depatux-M/Placebo.

If an incomplete onset date is collected for an AE, the AE will be assumed to be treatment-emergent unless there is evidence that confirms that is it not.

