11.0 Safety Analyses

11.1 General Considerations

Safety analysis will be carried out in the safety population. For most the safety endpoints (e.g., AEs, lab values, vital sign values and ECG values) except for TOE assessments, only the treatment emergent (TE) assessments (as defined in Section 7.3) will be included in the analyses. Incidence of TEAEs and treatment emergent lab abnormalities will be summarized in chemo-radiation phase and adjuvant phase separately and also in the overall study. A summary of continuous safety endpoints (e.g., change from baseline values in laboratory values, vital signs parameters) will include the mean, standard deviation, median and range. In the context of change from baseline analyses, summary of baseline and post-baseline data will also be provided. Categorical safety endpoints (e.g., incidence of AEs, incidence of potentially clinically significant values) will be summarized using frequencies and percentages. All the analyses will be carried out by treatment groups.

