The number and percentage of subjects experiencing TEAEs will be tabulated according to the primary MedDRA system organ class (SOC) and MedDRA preferred term (PT) for each treatment group. Subjects reporting more than one adverse event for a given MedDRA PT will be counted only once for that term. Subjects reporting more than one type of adverse event within a MedDRA SOC will be counted only once for that SOC. Subjects reporting more than one type of adverse event will be counted only once in the overall total.

AEs by Preferred Term

The number and percentage of subjects experiencing adverse events will be tabulated according to the MedDRA PT for each treatment group. Subjects reporting more than one AE for a given MedDRA PT will be counted only once for that term.

AEs by Maximum Severity

Adverse events will be summarized by SOC, PT and maximum severity per NCI CTCAE v.4 grading in each treatment arm. If a subject has an AE with unknown severity, then the subject will be counted in the severity category of "unknown," unless the subject does not have another occurrence of the same AE with a severity present. In addition, Grade 3 or higher AE and Grade 4 or higher events will also be summarized by SOC and PT.

AEs by Relationship

Adverse events possibly related to Depatux–M, TMZ, and radiotherapy as assessed by the investigator, will be summarized separately in each treatment arm. Following summaries

will be presented for the AEs possibly related to Depatux-M, TMZ, and radiotherapy, separately:

- Summary of AE by PT (possibly related to Depatux-M and TMZ only)
- Summary of AE by SOC and PT (possibly related to Depatux-M and TMZ only)
- Summary of Grade 3 or higher AE by SOC and PT
- Summary of Grade 4 or higher AE by SOC and PT
- Summary of SAE by SOC and PT
- Summary of Depatux-M/Placebo discontinuation by SOC and PT (possibly related to Depatux-M only)
- Summary of TMZ discontinuation by SOC and PT (possibly related to TMZ only)

If a subject has an AE with unknown relationship, then the subject will be counted in the relationship category of "unknown," unless the subject does not have another occurrence of the same AE with a relationship present.

AE of special interest (AESI)

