11.4.1 Variables and Criteria Defining Abnormality

NCI CTCAE v. 4 grading criteria for laboratory abnormalities are shown in [Table 9](#) and [Table 10](#).

Table 9. Criteria for NCI CTCAE Grades for Laboratory Values Hematology Variables

	Units	NCI CTCAE Grade ≥ 3		NCI CTCAE Grade ≥ 4	
		Low	High	Low	High
Hematology Variables					
Hemoglobin	g/L	< 80	> ULN + 40		
White blood cell count	$10^9/L$	< 2		< 1	
Neutrophil count	$10^9/L$	< 1		< 0.5	
Lymphocyte count	$10^9/L$	< 0.5		< 0.2	
Absolute Platelet count	$10^9/L$	< 50		< 25	
Coagulation Variables					
INR increased	ratio		> $2.5 \times \text{ULN}^*$		

* Or baseline if on anticoagulation.

Table 10. Criteria for NCI CTCAE Grades for Laboratory Values - Chemistry Variables

Chemistry Variables	Units	NCI CTCAE Grade ≥ 3		NCI CTCAE Grade ≥ 4	
		Low	High	Low	High
Creatinine	mcmol/L		$> 3 \times \text{ULN}$		$> 6 \times \text{ULN}$
Total bilirubin	mcmol/L		$> 3 \times \text{ULN}$		$> 10 \times \text{ULN}$
Alanine aminotransferase (ALT/SGPT)	U/L		$> 5 \times \text{ULN}$		$> 20 \times \text{ULN}$
Aspartate aminotransferase (AST/SGOT)	U/L		$> 5 \times \text{ULN}$		$> 20 \times \text{ULN}$
Alkaline phosphatase (ALP)	U/L		$> 5 \times \text{ULN}$		$> 20 \times \text{ULN}$
Gamma glutamyl transferase (GGT)			$> 5 \times \text{ULN}$		$> 20 \times \text{ULN}$
Sodium	mmol/L	< 130	> 155	< 120	> 160
Potassium	mmol/L	< 3	> 6	< 2.5	> 7
Calcium	mmol/L	< 1.75	> 3.1	< 1.5	> 3.4
Glucose	mmol/L	< 2.2	> 13.9	< 1.7	> 27.8
Cholesterol	mmol/L		> 10.34		> 12.92
Triglycerides	mmol/L		> 5.7		> 11.4
Albumin	g/L	< 20			
Magnesium	mmol/L	< 0.4	> 1.23	< 0.3	> 3.3

Definition of Potentially Clinically Significant Laboratory Values

Laboratory values will be considered as potentially clinically significant if they are Grade 3 or higher as shown in [Table 4](#) and [Table 5](#), with the following exceptions:

- GGT: Grade 4
- Total bilirubin: $> 2 \times \text{ULN}$
- Concurrent ALT or AST $> 3 \times \text{ULN}$ and total bilirubin $\geq 2 \times \text{ULN}$

- Concurrent ALT or AST $> 3 \times \text{ULN}$, ALP $< 2 \times \text{ULN}$ and total bilirubin $\geq 2 \times \text{ULN}$

The maximum ratio relative to the ULN will be used to determine if subjects met the criteria listed above. The ALT, AST, and total bilirubin values need to be concurrent (i.e., collected on same date) and should be collected within 49 days following the last dose date of any study drug in order to meet the defined criteria.

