11.5.2 Statistical Methods

Vital sign parameters (diastolic/systolic blood pressure, pulse rate, and body temperature) and body weight will be descriptively summarized by treatment groups. For each of the vital signs parameters, the following outputs will be produced:

- Summary of vital signs parameters at each scheduled visit
- Summary of changes from baseline at each post-baseline visit along with treatment group difference
- Summary of subjects with post baseline values meeting criteria for potentially clinically significant Vital Signs values

Change from baseline analyses will be summarized at each post-baseline visit and treatment group difference will be reported.

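### Taken as written, SAP 11.4.2 judges low-side laboratory limits by each subject's highest value, so a transient Grade 3 or worse low value can go uncounted in one descriptive safety table

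*SAP*

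**What the plan says.** SAP 11.4.1 defines the PCS criterion by grade: "Laboratory values will be considered as potentially clinically significant if they are Grade 3 or higher as shown in" the CTCAE tables, with stated exceptions for GGT and for bilirubin and combined liver tests. The grading limits are in Tables 9 and 10, which have both low and high columns.

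SAP 11.4.2 then lists the outputs for each continuous laboratory parameter. The one at issue is the per-arm count: "The number and percentage of subjects with maximum treatment-emergent laboratory values meeting the potentially clinically significant criteria (excluding hepatic tests". The bullet just before it is worded differently: "Shifts from baseline grades to worst post-baseline grades (only for the parameters where CTCAE grading is possible". The same list ends with a listing of laboratory values for subjects with PCS values, which has no maximum restriction.

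No sentence in SAP 11.4 gives a minimum rule for low limits. SAP 11.4.1 does say that the maximum ratio to the upper limit of normal decides whether criteria are met. That sentence follows the liver-test exceptions and may apply only to them. It gives no low-side rule in any case.

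SAP 11.1 limits laboratory analyses to treatment-emergent assessments and states the general aim: "Categorical safety endpoints (e.g., incidence of AEs, incidence of potentially clinically significant values) will be summarized using frequencies and percentages". SAP 7.3 defines treatment-emergent as "all newly occurring or worsening safety observation with onset at or following the initiation (date and time) of any study drug", up to 49 days after the last dose of Depatux-M or placebo.

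**The concern.** A maximum detects values that are too high. It falls below a low limit only if every included value does. Cytopenias under temozolomide are usually transient, and the protocol's dosing rules build in recovery. Protocol 8.3.1 withholds concomitant temozolomide until neutrophils reach 1.5 and platelets 100 (×10⁹/L), and protocol 8.3.2 requires the same levels on Day 1 of each adjuvant cycle. A subject who has a nadir and resumes therefore tends to have a later value well above the Grade 3 limit.

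Incidence of laboratory abnormalities is a named safety endpoint (SAP 5.3.4) and comparative safety is a stated objective (protocol 2.2). Thrombocytopenia is a listed potential toxicity of ABT-414 (protocol 8.1). It was also among the Grade 3 or higher events reported more often on ABT-414 at the interim analysis (protocol 1.0). Platelets have only a low limit, so the literal rule works worst on a variable where a per-arm laboratory count is of real interest.

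**Working it through.** The plan states no figure on this point, so there is none to reproduce. The check is a count of limits, a statement of the rule and a worked example.

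**Count of limits** (SAP Tables 9 and 10, Grade ≥ 3 columns)

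- The tables hold 6 + 14 = 20 variables. Remove ALT, AST, ALP and total bilirubin, the four liver measures named in protocol 8.4, and INR, which SAP Table 8 lists as screening only: 20 − 5 = 15. If GGT is also treated as hepatic, 14 remain. SAP 11.4.2 does not list the hepatic tests, so both figures are shown.
- Low limit only, 5 variables: WBC (< 2), neutrophils (< 1), lymphocytes (< 0.5), platelets (< 50), albumin (< 20).
- Low and high limits, 6 variables: hemoglobin (low < 80), sodium (< 130), potassium (< 3), calcium (< 1.75), glucose (< 2.2), magnesium (< 0.4).
- High limit only: creatinine, cholesterol and triglycerides (3), plus GGT if it is not hepatic (4).

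| | GGT hepatic | GGT not hepatic |
|---|---|---|
| Variables with a low limit | 11 of 14 | 11 of 15 |
| Low limits, 5 + 6 | 11 | 11 |
| High limits | 6 + 3 = 9 | 6 + 4 = 10 |
| Low limits as a share of all limits | 11 of 20 | 11 of 21 |

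**Rule**

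For a low limit L, the literal rule counts a subject if max(values) < L, that is, if all included values are below L. The intended event is min(values) < L. A subject is missed exactly when min < L ≤ max.

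**Example**

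The values are assumed: platelets 150 at baseline, then 40, then 80 (×10⁹/L), with L = 50. A baseline of 150 meets the eligibility requirement of at least 100 (protocol 3.1).

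| Reading of treatment-emergent | Values included | Maximum | Counted as written? | Minimum | Counted with minimum? |
|---|---|---|---|---|---|
| Worse than baseline | 40, 80 | 80 | No (80 ≥ 50) | 40 | Yes |
| All on-treatment values, adding a recovered 120 | 40, 80, 120 | 120 | No | 40 | Yes |
| Worse than the preceding value, or only the abnormality itself | 40 | 40 | Yes (40 < 50) | 40 | Yes |

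The count fails under the first two readings and not under the third. SAP 7.3 does not say which reference worsening is judged against. A minimum gives the right answer under all three.

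**Against the neighbouring output**

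In the first two rows the PCS table counts 0 and the worst-grade shift table counts 1 for the same subject.

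**The case against.** The strongest reply is that *maximum* was meant as maximum grade. PCS is itself defined by grade. Protocol 14.4 uses the word that way for laboratory data: "Shifts in laboratory values from baseline NCI CTCAE grades to maximum and final post-baseline grades will be assessed". The SAP's adverse event tables use "maximum severity per NCI CTCAE v.4 grading in each treatment arm". Low-only limits in Table 9 would make little sense for an output that could count them only when every value was low, and SAP 11.1 can be read as the general rule that settles loose wording. This is a plausible account of intent. It does not repair the text. The bullet refers to values, while the bullet before it refers to worst grades. The vital-signs output, which also has low limits (heart rate and temperature in SAP Table 11), uses no maximum: "Summary of subjects with post baseline values meeting criteria for potentially clinically significant Vital Signs values". A programmer following the wording could take a numeric maximum.

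The second reply is that the information is reported elsewhere, and most of this stands. For the five low-only variables, the worst-grade shift table gives the correct Grade ≥ 3 count per arm. The PCS listing shows the individual values, and thrombocytopenia and neutropenia are adverse events of special interest (SAP 11.2.1). Some gaps remain. The listing gives no per-arm n (%), and SAP 11.4.2 does not say whether the shift table separates low from high for the two-sided variables. Protocol 7.2.1.1 makes a laboratory change an adverse event only under certain conditions.

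A reader might infer that the count fails however treatment-emergent is read. The third row of the example shows otherwise. A reader might also infer that the plan would hide a cytopenia signal. The other outputs just listed do not allow that conclusion.

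**Conclusion.** The wording is wrong as it stands, and the consequence is minor. Taken literally, a Grade ≥ 3 low value is missed whenever another included treatment-emergent value is at or above the limit. This applies to 11 low limits, affecting 11 of 14 variables and 11 of 20 limits if GGT is hepatic, or 11 of 15 and 11 of 21 if it is not. The count of 11 treats albumin as non-hepatic, in line with the four measures in protocol 8.4.

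The conclusion rests on two assumptions: that *maximum* is applied to values, and that treatment-emergent values are those worse than baseline or all on-treatment values. Only this descriptive per-arm n (%) is affected. No efficacy analysis, interim decision or data collection changes. The number of subjects missed cannot be computed. The interim figures in protocol 1.0 concern adverse events and do not supply a laboratory rate.

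**What to change.** In the PCS-count bullet of SAP 11.4.2, base the count on *the worst treatment-emergent value in the direction of the criterion (the minimum for a low limit, the maximum for a high limit)*. Report low and high separately for hemoglobin, sodium, potassium, calcium, glucose and magnesium.

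Two optional edits fit the same revision. Naming the excluded hepatic tests would settle where GGT belongs. The grade reference in SAP 11.4.1 should point to Tables 9 and 10; it now points to Tables 4 and 5, which are visit windows for vital signs and KPS.

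The main change costs one phrase in the SAP and one programming parameter, with no new data.

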11.5 Analysis of Vital Signs

11.5.1 Variables and Criteria Defining Abnormality

Pre-defined criteria for potentially clinically significant vital signs values are given in [Table 11](#).

Table 11. Criteria for Potentially Clinically Significant vital signs Values

Vital Signs Variables	Criterion	Definition of Potentially Clinically Significant Values
Systolic blood pressure	High	Value \geq 160 mmHg
Diastolic blood pressure	High	Value \geq 100 mmHg
Heart rate	Low	Value \leq 50 bpm
	High	Value \geq 120 bpm
Temperature	Low	Value \leq 32°C
	High	Value $>$ 40°C

11.5.2 Statistical Methods

Vital sign parameters (diastolic/systolic blood pressure, pulse rate, and body temperature) and body weight will be descriptively summarized by treatment groups. For each of the vital signs parameters, the following outputs will be produced:

- Summary of vital signs parameters at each scheduled visit
- Summary of changes from baseline at each post-baseline visit along with treatment group difference
- Summary of subjects with post baseline values meeting criteria for potentially clinically significant Vital Signs values

Change from baseline analyses will be summarized at each post-baseline visit and treatment group difference will be reported.

11.6 Analysis of ECG parameters

ECG will be performed at screening, final visit and when clinically indicated. These ECG values will be summarized by visit and treatment group. Change from baseline at each post-baseline visit will also be summarized using shift table.

13.0 Appendix

Appendix I: Determining deterioration in HVLt-R Total Recall score and COWA FAS score

Raw Score will be standardized using the published age-specific normative data from a healthy population as follows.

$$\text{Z score} = \frac{\text{Raw Score} - \text{Mean norm Score}}{\text{Norm standard deviation}}$$

At each post-baseline assessment, change in raw score relative to baseline will be calculated and categorized as declined or not using the reliable change index (RCI) criterion based on the raw scores. The RCI is derived from the standard error of measurement of each test and represents the 90% confidence interval for the difference in raw score from baseline to the next assessment that would be expected if no real change occurred.^{2,14}

$$\text{RCI} = 1.64(\text{SEdiff}), \text{ where } \text{SEdiff} = [2(\text{SEM}^2)]^{1/2} \text{ and } \text{SEM} = \text{SD}[(1 - r)^{1/2}]$$

SEdiff is the standard error of difference, SEM is the standard error of measurement, SD is the standard deviation, and r is the test-retest reliability statistic. All RCI thresholds were rounded to the nearest whole number. For HVLt-R total score and COWA-FAS score, $r = 0.74$ and 0.70 will be used, respectively.⁴ Deterioration in raw score should be compared against the RCI threshold to determine the meaningful deterioration.

Appendix II: Summary of RANO response criteria

Tumor progression will be assessed using the RANO criteria as outlined below according to Wen, et al,³⁰ "Updated Response Assessment Criteria for High-Grade Gliomas: Response Assessment in Neuro-Oncology Working Group." Note: Only PFS data will be analyzed in this study.

Table 1. Criteria for Determining First Progression Depending on Time from Initial Chemoradiotherapy

First Progression	Definition
Progressive disease < 12 weeks after completion of chemoradiotherapy	
Progression can only be defined using diagnostic imaging if there is new enhancement outside of the radiation field (beyond the high-dose region or 80% isodose line) or if there is unequivocal evidence of viable tumor on histopathologic sampling (e.g., solid tumor areas [i.e., > 70% tumor cell nuclei in areas], high or progressive increase in MIB-1 proliferation index compared with prior biopsy, or evidence for histologic progression or increased anaplasia in tumor).
 
Note: Given the difficulty of differentiating true progression from pseudoprogression, clinical decline alone, in the absence of radiographic or histologic confirmation of progression, will not be sufficient for definition of progressive disease in the first 12 weeks after completion of concurrent chemoradiotherapy.

Progressive disease ≥ 12 weeks after chemoradiotherapy completion	
 1. New contrast-enhancing lesion outside of radiation field on decreasing, stable, or increasing doses of corticosteroids. 2. Increase by ≥ 25% in the sum of the products of perpendicular diameters between the first post-radiotherapy scan, or a subsequent scan with smaller tumor size, and the scan at 12 weeks or later on stable or increasing doses of corticosteroids. 3. Clinical deterioration not attributable to concurrent medication or comorbid conditions is sufficient to declare progression on current treatment but not for entry onto a clinical trial for recurrence. 4. For patients receiving anti-angiogenic therapy, significant increase in T2/FLAIR non-enhancing lesion may also be considered progressive disease. The increased T2/FLAIR must have occurred with the patient on stable or increasing doses of corticosteroids compared with baseline scan or best response after initiation of therapy and not be a result of comorbid events (e.g., effects of radiation therapy, demyelination, ischemic injury, infection, seizures, post-operative changes, or other treatment effects).

FLAIR = fluid-attenuated inversion recovery

Pseudoprogession and Radiation Effects

The proposed new response criteria suggest that within the first 12 weeks of completion of radiotherapy, when pseudoprogession is most prevalent, progession can only be determined if the majority of the new enhancement is outside of the radiation field (for example, beyond the high-dose region or 80% isodose line) or if there is pathologic confirmation of progressive disease. It is recognized that the proposed histologic criteria have important limitations, but they provide guidance on the type of findings that are suggestive of progressive disease. For patients in whom pseudoprogession cannot be differentiated from true tumor progession, enrollment onto trials for recurrent gliomas should not be permitted. Patients who remain clinically stable and/or are suspected to have pseudoprogession based on metabolic or vascular imaging should continue with their current therapy.

Enhancement as a Result of Surgery and Other Therapies

Increased enhancement often develops in the wall of the surgical cavity 48 to 72 hours after surgery. To avoid interpretation of post-operative changes as residual enhancing disease, a baseline MRI scan should ideally be obtained within 24 to 48 hours after surgery and no later than 72 hours after surgery. The inclusion of diffusion weighted imaging in the immediate post-operative MRI scan can be helpful in determining whether new enhancement developing in the subsequent weeks or months is caused by sequelae of ischemia or by tumor recurrence. In addition, a transient increase in enhancement that can be difficult to distinguish from recurrent disease can also occur after locally administered therapies. These include chemotherapy wafers, immunotoxins delivered by convection enhanced delivery, regionally administered gene and viral therapies, immunotherapies, and focal irradiation with brachytherapy and stereotactic radiosurgery. Imaging modalities such as perfusion imaging, magnetic resonance spectroscopy, and positron emission tomography scans may sometimes be helpful in differentiating treatment effects from recurrent tumor. However, no imaging modality currently has sufficient specificity to conclusively differentiate recurrent tumor from treatment effects, and surgical sampling may occasionally be needed to obtain a definitive diagnosis.

Definition of Clinical Deterioration

The definition of clinical deterioration is left to the discretion of the treating physician, but it is recommended that a decline in the KPS from 100 or 90 to 70 or less, a decline in KPS of at least 20 from 80 or less, or a decline in KPS from any baseline to 50 or less, for at least 7 days, be considered neurologic deterioration unless attributable to comorbid events or changes in corticosteroid dose. Similarly, a decline in the Eastern Cooperative Oncology Group and WHO performance scores from 0 or 1 to 2 or 2 to 3 would be considered neurologic deterioration.

For those subjects who have measurable disease post resection, RANO criteria for assessment of CR, PR, SD and PD can be applied. See the below tables for the definitions to be used.

Definition of Radiographic Response

Radiographic response should be determined in comparison to the tumor measurement obtained at pretreatment baseline for determination of response, and the smallest tumor measurement at either pretreatment baseline should be used for determination of progression. The criteria for radiographic changes after therapy are listed in Table 2. In the event that the radiographic changes are equivocal and it is unclear whether the patient is stable or has developed progressive disease, it is permissible to continue treatment and observe the patient closely, for example at 4 week intervals. If subsequent imaging studies demonstrate that progression has occurred, the date of progression should be the date of the scan at which this issue was first raised. The determination of radiographic response after treatment with agents that affect vascular permeability is particularly difficult. In these patients, consideration should be given to performing a second scan at 4 weeks to confirm the presence of response or stable disease. All measurable and nonmeasurable lesions should be assessed using the same techniques as at baseline. Ideally, patients should be imaged on the same MRI scanner, or at least with the same magnet strength, for the duration of the study to reduce difficulties in interpreting changes.

Patients with nonmeasurable enhancing disease whose lesions have significantly increased in size and become measurable (minimal bidirectional diameter of ≥ 10 mm and visible on at least two axial slices that are preferably, at most, 5 mm apart with 0 mm skip) will also be considered to have experienced progression. The transition from a nonmeasurable lesion to a measurable lesion resulting in progression can theoretically occur with relatively small increases in tumor size (e.g., a 9×9 mm lesion [nonmeasurable] increasing to a 10×11 mm lesion [measurable]). Ideally, the change should be significant (> 5 mm increase in maximal diameter or $\geq 25\%$ increase in sum of the products of perpendicular diameters of enhancing lesions). In general, if there is doubt about whether the lesion has progressed, continued treatment and close follow-up evaluation will help clarify whether there is true progression. If there is uncertainty regarding whether there is progression, the patient may continue on treatment and remain under close observation (e.g., evaluated at 4-week intervals). If subsequent evaluations suggest that the patient is in fact experiencing progression, then the date of progression should be the time point at which this issue was first raised.

Table 2. Summary of the Proposed RANO Response Criteria

Criterion	CR	PR	SD	PD
T1 gadolinium enhancing disease	None	$\geq 50\% \downarrow$	$< 50\% \downarrow$ but $< 25\% \uparrow$	$\geq 25\% \uparrow^*$
T2/FLAIR	Stable or \downarrow	Stable or \downarrow	Stable or \downarrow	\uparrow^*
New Lesion	None	None	None	Present*
Corticosteroids	None	Stable or \downarrow	Stable or \downarrow	NA**
Clinical status	Stable or \uparrow	Stable or \uparrow	Stable or \uparrow	\downarrow^*
Requirement for response	All	All	All	Any*

RANO = Response Assessment in Neuro-Oncology; CR = complete response; PR = partial response; SD = stable disease; PD = progressive disease; FLAIR = fluid-attenuated inversion recovery; NA = not applicable

* Progression occurs when this criterion is present.

** Increase in corticosteroids alone will not be taken into account in determining progression in the absence of persistent clinical deterioration.

